### 9.4.3 Sensitivity and Supplementary Analyses for Secondary Efficacy Endpoints

Not applicable.

### 9.4.4 Supportive Secondary Efficacy Endpoints and Analyses

Not applicable.

## 9.5 Additional Efficacy Analyses

Additional efficacy endpoints described in Section 3.3 will be analyzed at all visits assessed using the same methods listed in above and Section 9.2. The attributes of the estimands corresponding to the additional efficacy endpoints are summarized in Table 3.

**Table 3. Summary of the Estimand Attributes of the Additional Efficacy Endpoints**

For binary endpoint:

Estimand Label	Attributes of the Estimand				
	Treatment	Endpoint	Population	Handling of Intercurrent Events	Statistical Summary
Binary Additional Variable (Composite)	ABBV-154 vs. Placebo	Achievement of each binary additional endpoint respectively	ITT	IE1: Initiation of rescue medication IE2: Initiation of immunomodulator IE3: Initiation of violation of protocol-allowed systemic glucocorticoid use  Subjects will be considered as non-responders for visits after ICEs.	Difference in proportion of subjects achieving each binary additional endpoint

For continuous endpoint:

Estimand Label	Attributes of the Estimand				Statistical Summary
	Treatment	Endpoint	Population	Handling of Intercurrent Events	
Continuous Additional Variable (Composite)	ABBV-154 vs. Placebo	Change from Baseline in each respective continuous additional endpoint	ITT	IE1: Initiation of rescue medication IE2: Initiation of immunomodulator IE3: Initiation of violation of protocol-allowed systemic glucocorticoid use  Efficacy assessments after the start of IE will not be included in the analyses, and visits after IE will be handled by MMRM.	Difference in the mean change from Baseline in each continuous additional endpoint

## 9.6 Dose-Response Modeling for ABBV-154

The dose-response relationship among ABBV-154 dose groups and the placebo group will be characterized for the primary endpoint using the Multiple Comparison Procedure – Modeling (MCP-Mod) method [Pinheiro 2006, Bretz 2005]. The summary level response rates based on the primary analysis approach above will be used, and ADDPLAN DF software will be used to perform the MCP-Mod analyses.

A set of 6 pre-specified standardized candidate dose-response models, as described in Table 4 will be utilized to examine the dose-response relationship. A statistically significant dose-response relationship will be declared if at least one model is identified by the MCP-Mod method to be statistically significant at two-sided  $\alpha = 0.1$ . The fitted dose-response curves will be presented graphically for all statistically significant models along with 95% confidence bands. The minimum effective dose (MED) will be identified for each statistically significant model based on the pre-specified clinical meaningful

target of 22%. The weighted MED across all significant models will be calculated, with weight being the inverse of each candidate dose-response model AIC.

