The 3 SC dosing regimens (40 mg EOW, 150 mg EOW, and 340 mg EOW) selected for evaluation in this study are reasonably separated across a wide dose range to cover the potential clinical efficacious doses and to enable a robust characterization of dose-/exposure-response relationships for Phase 3 dose selection. All selected doses are within the range of single doses safely tested in the ABBV-154 first-in-human study (highest dose 600 mg intravenous) and are adequately covered by safety margins provided by chronic toxicology studies. Projected ABBV-154 and payload safety margins for the high dose of 340 mg SC EOW are at least 24-fold and 10-fold, respectively, based on predicted ABBV-154 human exposures and the observed toxicokinetic data in the 26-week cynomolgus monkey study.

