The primary endpoint is the time to flare. The time origin is the first dose of study drug and the time of first flare will be used for the analysis. Comparison of the primary endpoint will be made between each ABBV-154 dose and placebo using the log-rank test adjusting for stratification factors. The point and CI estimate of median time to flare and flare-free rate for each group will be reported based on Kaplan-

Meier curves. Hazard ratio and its corresponding CI for each ABBV-154 group versus placebo will be estimated using Cox regression analysis adjusting for stratification factors.

One supplementary analysis for the primary endpoints is to test a prespecified set of dose-response models among ABBV-154 dose groups and the placebo group at Week 24 using the Multiple Comparison Procedure – Modeling (MCP-Mod) method.

Summary and Analysis of Secondary Endpoints

Analysis of secondary endpoints are described above.

Summary and Analysis of Additional Efficacy Endpoints

Analysis of additional efficacy endpoints are described above.

Subgroup Analysis for Efficacy

To evaluate the consistency of efficacy across demographic and other baseline characteristics, the following subgroup analysis will be performed on the primary endpoint:

- Baseline glucocorticoid use (≥ 10 mg/day; < 10 mg/day prednisone equivalent)
- Length of prior glucocorticoid treatment for PMR (≤ 1 year; > 1 year)
- Age (\leq median; $>$ median)
- Sex (female; male)
- Race (white; nonwhite)

In addition, change from Baseline in glucocorticoid dose at Week 24 will be analyzed by the following subgroup:

- Glucocorticoid status at Week 24 (glucocorticoid free; not glucocorticoid free)

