## 2.4 Sample Size Determination

A total of 37 flares in the highest dose of ABBV-154 group and placebo group would provide more than 90% power to detect a hazard ratio of 0.296 at 2-sided significance level of 0.1. The hazard ratio of 0.296 is determined under the assumption that flares would occur during the tapering and within 12 weeks after the end of tapering (up to Week 36), and 70% and 30% of subjects will remain flare-free by Week 36 in the highest dose of ABBV-154 group and placebo group, respectively.

Based on an  $E_{\max}$  model with  $ED_{50}$  of 150 mg, a total of 74 flares are expected for the Primary Analysis. A sample size of 40 subjects in each of the ABBV-154 and placebo arms is planned to ensure appropriate accrual of flares. A sample size re-estimation may be considered at an interim analysis prior to unblinding of the study team. The sample size increase will be capped at approximately 100 subjects.

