**Table 4. Candidate Models**

Model	$f(d, \theta)$ $d = \text{dose},$ $\theta = \text{Model Parameters}$	$f^0(d, \theta)$ Standardized Model	Initial Value(s) for Parameter(s)*
Linear	$E_0 + \delta d$	$d$	NA
Exponential	$E_0 + E_1 \left[ \exp\left(\frac{d}{\delta}\right) - 1 \right]$	$\exp\left(\frac{d}{\delta}\right) - 1$	$\delta = 680$
Logistic	$E_0 + \frac{E_{max}}{1 + \exp\left(\frac{ED_{50} - d}{\delta}\right)}$	$\frac{1}{1 + \exp\left(\frac{ED_{50} - d}{\delta}\right)}$	$ED_{50} = 150, \delta = 64.5$
E max	$E_0 + \frac{E_{max}d}{ED_{50} + d}$	$\frac{d}{ED_{50} + d}$	$ED_{50} = 83.9$
sigE Max	$E_0 + \frac{E_{max}d^h}{ED_{50}^h + d^h}$	$\frac{d^h}{ED_{50}^h + d^h}$	$ED_{50} = 150, h = 3.6$
Quadratic	$E_0 + \beta_1 d + \beta_2 d^2$	$d + \frac{\beta_2}{ \beta_1 } d^2$	$\delta = -0.001$

\* For Exponential model, the initial value was determined based on the assumption that ABBV-154 340 mg EOW will achieve 95% of the maximum efficacy of ABBV-154. For Logistic, Emax, sigEMax, and Quadratic model, the initial values were determined based on the assumption that ABBV-154 340 mg EOW and ABBV-154 150 mg EOW will achieve 95% and 50% of the maximum efficacy of ABBV-154, respectively.

Steps of MCP-Mod:

1. Choose a candidate set of models as in Table 4.
2. Compute the optimum contrast for each model.
3. Use contrast test to find all significant models while preserving family-wise error rate (FWER).

4. Use all significant models to make inference about the weighted target dose of interest.

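### SAP 9.6 averages the model MEDs with 1/AIC weights, which depend on an unstated likelihood constant; the weighted MED is distorted mainly if the response plateaus early

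*SAP*

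**What the plan says.** SAP 9.6 fits six candidate dose-response models at 0, 40, 150 and 340 mg. On input and software it says: "The summary level response rates based on the primary analysis approach above will be used, and ADDPLAN DF software will be used". No likelihood or AIC convention is given.

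The SAP then says: "The minimum effective dose (MED) will be identified for each statistically significant model", against a target of 22%. It continues "The weighted MED across all significant models will be calculated", "with weight being the inverse of each candidate dose-response model AIC". The last of the MCP-Mod steps under Table 4 is "Use all significant models to make inference about the weighted target dose of interest". No other weight formula appears, and there is no rule for a significant model whose curve stays below the target up to 340 mg.

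Protocol 4.2 says the dose range was chosen "to enable a robust characterization of dose-/exposure-response relationships for Phase 3 dose selection". Protocol 7.4 sets the status and the time point (Week 24): "One supplementary analysis for the primary endpoints is to test a prespecified set of dose-response models".

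**The concern.** Adding the same constant to every AIC leaves the comparison of models unchanged, but it changes every 1/AIC weight. Two programmers who fit the same curves to the same data can therefore report different weighted MEDs, depending only on whether a likelihood constant is kept or dropped. When the AICs are large compared with their differences, a model that the data contradict keeps almost the same weight as the best one. When they are negative, the ordering reverses. When they have mixed signs, some weights are negative.

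At stake is the one averaged target dose of an analysis meant to inform Phase 3 dose selection. A missing MED is a smaller gap of the same kind: after unblinding, the analyst would have to choose whether to drop, cap or extrapolate.

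**Working it through.** **Inputs.** Arms of 40 at 0, 40, 150 and 340 mg; the six Table 4 families; a 22% target, read as 22 percentage points over placebo. SAP 2.4 assumes that "70% and 30% of subjects will remain flare-free by Week 36" on the top dose and placebo respectively. No Week 24 rates are given, so these Week 36 rates were used. Table 4 gives only initial values, so parameter bounds are assumed: ED50 0.34-510 mg, h 0.5-10, logistic delta 3.4-170, exponential delta 34-3400 or, as a variant, also negative.

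**The plan's own figures.** The documents give no figure for the weights or the weighted MED. The inputs do reproduce:
- hazard ratio ln(0.70)/ln(0.30) = 0.296;
- logistic delta (340 - 150)/ln 19 = 64.5;
- sigmoid h = ln 19/ln(340/150) = 3.6;
- Emax ED50 = mean of 17.9 and 150 = 83.9.

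**Early-plateau example.** Assumed flare-free counts are 12, 26, 28 and 28 of 40. All six contrasts are significant (z 2.88-4.11, critical value 1.84). Binomial maximum likelihood, delta > 0, AIC = -2 log L + 2k without the binomial coefficient:

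| Model | AIC | 1/AIC weight | Akaike weight | MED (mg) |
|---|---|---|---|---|
| Linear | 213.15 | 0.163 | 0.007 | 280 |
| Exponential | 215.32 | 0.162 | 0.002 | 286 |
| Logistic | 206.40 | 0.169 | 0.199 | 23 |
| Emax | 204.41 | 0.170 | 0.539 | 8 |
| Sigmoid Emax | 206.40 | 0.169 | 0.199 | 32 |
| Quadratic | 209.03 | 0.167 | 0.053 | 73 |

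- 1/AIC: 0.163×280 + 0.162×286 + 0.169×23 + 0.170×8 + 0.169×32 + 0.167×73 = 115 mg. The unweighted mean is 117 mg.
- Akaike, w = exp(-(AIC - 204.41)/2), normalised: 0.007×280 + 0.002×286 + 0.199×23 + 0.539×8 + 0.199×32 + 0.053×73 = 22 mg.

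The two four-parameter models are nearly saturated on four doses, so their MEDs are loosely determined. Across fits the Akaike result is about 19-22 mg.

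**Dependence on the AIC convention (same counts, delta > 0).**

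| AIC convention | Best-to-worst weight ratio | 1/AIC MED (mg) |
|---|---|---|
| Binomial, coefficient dropped | 1.05 | 107-115 |
| Binomial, coefficient kept | 1.5 | 101 |
| Chi-square + 2k on four rates | 3.0 | 72-73 |
| n log(RSS/n) + 2k on four rates | reversed (all AICs negative) | about 174 |

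Under the first three conventions the Akaike ratio is about 230-430. Where a range is shown, it spans weighted least squares and maximum likelihood fits. Subtracting 180, 200 or 210 from every AIC in the first table moves the 1/AIC MED from 115 to 103, 74 and -40 mg. The Akaike result does not move. (Those three constants are illustrative; nothing suggests that ADDPLAN DF uses them.)

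With exponential delta of either sign, the 1/AIC MED is about 66-70 mg (binomial) or 45 mg (chi-square + 2k), against 18-19 mg.

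**Design-like counts (12, 17, 24, 28).** The result is 128-129 against 129-131 mg with delta > 0, and 109-111 against 115-116 mg with either sign.

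**Simulation.** 1,500 trials per shape, weighted least squares, rates 0.30 to 0.70, binomial and chi-square + 2k AIC. For Emax shapes the true MED is 0.22×ED50/(Emax - 0.22); for ED50 150, Emax = 0.40×490/340 = 0.576 and the MED is 93 mg. RMSE in mg, 1/AIC against Akaike:

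| True shape | delta > 0 | either sign |
|---|---|---|
| Emax, ED50 10 | 69-89 v 50-52 | 55-63 v 49 |
| Emax, ED50 25 | 74-86 v 63-64 | 58-62 v 57 |
| Emax, ED50 40 | 77-84 v 72-73 | 63-64 v 64-65 |
| Emax, ED50 83.9 | 72-74 v 73 | 62-63 v 67 |
| Emax, ED50 150 | 68-69 v 73-74 | 62-64 v 69 |

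Over both bounds, the sigmoid shape gives 43-49 against 50-52 and the linear shape 55-59 against 60-61.

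**No MED.** In these simulations 0.7-3.8% of significant fits never reached +22 points. It can happen without sampling noise. Converting the rates to Week 24 under a constant hazard (0.30^(24/36) = 0.448, 0.70^(24/36) = 0.788) with ED50 10, the exponential model is significant but has no MED.

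**The case against.** The strongest reply is about reach. The shapes that do harm lie outside the plan's assumptions: SAP 2.4 uses ED50 150, and Table 4 puts half the maximum effect at 150 mg. For those shapes, near-equal weighting is no worse and is slightly more accurate than Akaike weights. With four doses and two four-parameter models, equal weighting is a defensible choice. This stands, and it limits the severity. It does not rescue the rule: if equal weights were wanted, the SAP could say so, whereas 1/AIC gives them only on some likelihood scales.

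A second reply is that the SAP feeds summary-level rates to the software, which may point to a four-point AIC. That also stands. A reader might infer that the rule always reduces to a plain average in which bad models count fully; the documents do not support this, because they leave the scale open and only models that pass the contrast test enter.

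Third, the sizes rest on assumed counts and bounds. Allowing a negative exponential delta alone moves 115 to 70 mg. Moving one subject in the early-plateau example gives 64-124 mg with 1/AIC and 13-28 mg with Akaike weights (delta > 0). The Akaike MEDs there lie below the lowest active dose of 40 mg, so they are interpolations.

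Finally, the word inverse may be shorthand for what the software does. If so, the SAP does not describe the analysis that will be run, and the text still needs correcting.

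**Conclusion.** Wrong as written, minor. The weight rule depends on a constant that carries no information about fit and that the SAP does not fix. Simulated accuracy is clearly worse for an ED50 of about 10 mg, and at 25 mg mainly when the exponential delta is restricted to positive values. At 40 mg there is a smaller loss under that restriction and none without it. ED50 values of 10, 25 and 40 mg are stress cases, not design assumptions. For design-like shapes the rule costs little or nothing.

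A reader might infer that the wrong dose would go forward to Phase 3. The documents do not support that. No section makes the weighted MED a decision rule, MCP-Mod is supplementary, and the fitted curves and per-model MEDs are also produced and would show an early plateau. The log-rank tests, the contrast tests and those per-model results do not change.

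The figures assume 40 evaluable subjects per arm, Week 36 planning rates used at Week 24, and the stated parameter bounds.

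**What to change.** Replace the last sentence of the SAP 9.6 text before Table 4 with:

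> For each significant model, AIC_m = -2 log L_m + 2k_m, where L_m is the binomial likelihood of the Week 24 flare-free counts in the four arms at the fitted curve and k_m is the number of parameters. The weighted MED is the sum of w_m × MED_m, with w_m = exp(-(AIC_m - AIC_min)/2) normalised over significant models whose fitted curve exceeds its fitted placebo rate by at least 22 percentage points at some dose up to 340 mg. Significant models that do not reach the target are listed with their total Akaike weight, and the weighted MED is described as conditional on reaching the target.

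The likelihood has to be named. Akaike weights cancel additive constants but not a change of scale: on n log(RSS/n) + 2k, almost all the weight goes to a nearly saturated four-parameter model, and the design-like counts give about 85-87 mg instead of 129-131 mg.

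The cost is a few lines of text and one formula; no new data are needed. There are two downsides. The weights vary more when models fit about equally well, with RMSE up to about 7 mg higher (Emax ED50 83.9 and 150, sigmoid, linear). Leaving out models without a MED also pulls the average down slightly, which is why their total weight should be reported beside it.

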**Table 4. Candidate Models**

Model	$f(d, \theta)$ $d = \text{dose},$ $\theta = \text{Model Parameters}$	$f^0(d, \theta)$ Standardized Model	Initial Value(s) for Parameter(s)*
Linear	$E_0 + \delta d$	$d$	NA
Exponential	$E_0 + E_1 \left[ \exp\left(\frac{d}{\delta}\right) - 1 \right]$	$\exp\left(\frac{d}{\delta}\right) - 1$	$\delta = 680$
Logistic	$E_0 + \frac{E_{max}}{1 + \exp\left(\frac{ED_{50} - d}{\delta}\right)}$	$\frac{1}{1 + \exp\left(\frac{ED_{50} - d}{\delta}\right)}$	$ED_{50} = 150, \delta = 64.5$
E max	$E_0 + \frac{E_{max}d}{ED_{50} + d}$	$\frac{d}{ED_{50} + d}$	$ED_{50} = 83.9$
sigE Max	$E_0 + \frac{E_{max}d^h}{ED_{50}^h + d^h}$	$\frac{d^h}{ED_{50}^h + d^h}$	$ED_{50} = 150, h = 3.6$
Quadratic	$E_0 + \beta_1 d + \beta_2 d^2$	$d + \frac{\beta_2}{ \beta_1 } d^2$	$\delta = -0.001$

\* For Exponential model, the initial value was determined based on the assumption that ABBV-154 340 mg EOW will achieve 95% of the maximum efficacy of ABBV-154. For Logistic, Emax, sigEMax, and Quadratic model, the initial values were determined based on the assumption that ABBV-154 340 mg EOW and ABBV-154 150 mg EOW will achieve 95% and 50% of the maximum efficacy of ABBV-154, respectively.

Steps of MCP-Mod:

1. Choose a candidate set of models as in Table 4.
2. Compute the optimum contrast for each model.
3. Use contrast test to find all significant models while preserving family-wise error rate (FWER).

4. Use all significant models to make inference about the weighted target dose of interest.

## 9.7 Efficacy Subgroup Analyses

Subgroup analysis for the primary endpoint will be conducted by the subgroups specified below. The difference in the primary efficacy endpoint between the treatment groups in each subgroup will be assessed using the same approach for primary endpoint.

- Baseline glucocorticoid use ( $\geq 10$  mg/day;  $< 10$  mg/day prednisone equivalent)
- Length of prior glucocorticoid treatment for PMR ( $\leq 1$  year;  $> 1$  year)
- Age ( $\leq$  median;  $>$  median)
- Sex (female; male)
- Race (white; nonwhite)
- Time since most recent PMR flare prior to Baseline ( $\leq 12$  weeks;  $> 12$  weeks)

In addition, change from Baseline in glucocorticoid dose at Week 24 will be analyzed by the following subgroup. The difference in this endpoint between the treatment groups in each subgroup will be assessed using ANCOVA approach. Treatment difference and corresponding confidence interval will be used to summarize the result.

- Glucocorticoid status at Week 24 (glucocorticoid free; not glucocorticoid free)

If any subgroup has fewer than 10% of the total subjects, then the analysis for this subgroup will not be performed.

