- Subject is significantly noncompliant with study procedures, which would put the subject at risk for continued participation in the trial as determined by the Investigator or AbbVie TA MD.
- Subject is prematurely unblinded to study drug assignment by the investigator or AbbVie TA MD.
- Subject requires the addition of prohibited immunomodulatory medication for treatment of PMR.

- Diagnosis of GCA.

When the blinded study drug (ABBV-154/placebo) is discontinued, the Sponsor-supplied prednisone/prednisolone must also be discontinued. Prednisone/prednisolone may then be prescribed by the investigator, with dosing based on the investigator's judgement and in accordance with local standard of care. Medications prescribed by the investigator should be documented on the concomitant medication eCRF.

Additional requirements related to abnormal laboratory values and selected specific AEs (safety topics of interest) are located in Section 6.2.

COVID-19 Pandemic-Related Acceptable Protocol Modification

During the COVID-19 pandemic, it may be necessary to employ mitigation strategies to enable the investigator to ensure subject safety and continuity of care. Acceptable mitigation strategies are identified and included in the Operations Manual in [Appendix H](#).

The investigator should contact the sponsor medical contact before discontinuing a subject from the study for a reason other than "planned per protocol," to ensure all acceptable mitigation steps have been explored. Refer to the Operations Manual in [Appendix H](#) for details on how to handle study activities/procedures.

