If a subject has a suspected PMR flare at any time during the study, the flare should be confirmed as soon as possible, prior to initiating glucocorticoid rescue treatment. Flare may be confirmed at either a scheduled visit or unscheduled visit. Assessments performed at a visit for suspected flare are listed in Section 5.7 and in the Operations Manual (Appendix H). Additional assessments may be added per the investigator's medical judgement. PMR must be confirmed as the cause of flare by eliminating other causes of the subject's symptoms/signs such as infection or other underlying disease. Once flare is confirmed, glucocorticoid rescue should be administered with the dose and subsequent tapering at the discretion of the investigator, taking into consideration local standard of care, the subject's preflare and/or baseline dose, and not exceeding 15 mg/day. The investigator must record his/her recommendation to increase the prednisone/prednisolone dose due to PMR flare in the eCRF, regardless of whether or not the subject agrees to increase his/her dose. The specific dose of glucocorticoid rescue therapy taken by the subject should be documented in the eCRF.

While receiving open-label rescue treatment with prednisone/prednisolone, the subject should continue in the study and receive blinded study drug (ABBV-154/placebo) unless the subject meets the study drug discontinuation criteria (see Section 5.5).

If a subject remains on prednisone/prednisolone up to the Week 52 visit, the subject will take the last dose of Sponsor-supplied prednisone/prednisolone on the day prior to the Week 52 or on the day of the Week 52 visit and may restart individually-sourced prednisone equivalent on or after the day of the Week 52 visit, under the medical guidance of the investigator.

Addition of immunomodulators other than glucocorticoid rescue, as outlined above, are not permitted for rescue. If the investigator determines it is in the best interest of the subject to start an immunomodulator, the subject must discontinue study drug treatment (ABBV-154/placebo and sponsor-supplied prednisone/prednisolone). Any subsequent medications prescribed by the investigator should be documented on the concomitant medication eCRF.

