### **8.0 Handling of Potential Intercurrent Events for the Primary and Secondary Endpoints**

The primary efficacy endpoint (defined in Section 3.1) will be analyzed based on the ITT population and subjects will be censored at the time of the last available assessment, initiation of immunomodulator, or violation of protocol-allowed systemic glucocorticoid use.

The categorical secondary efficacy endpoint (defined in Section 3.2) will be analyzed based on the ITT population and the following methods will be used to address the potential intercurrent events:

- Subjects will be considered as not achieving the response after the initiation of rescue medication, immunomodulator or violation of protocol-allowed systemic glucocorticoid use.

The continuous secondary efficacy endpoints (defined in Section 3.2) will be analyzed based on the ITT population and the following methods will be used to address the potential intercurrent events:

- No intercurrent event will be considered in the analysis of glucocorticoid dose.

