placebo. Note that measurements will be considered as missing after the start of confounding medication before MI. Regardless of MI imputed values, subjects after receiving confounding medication will be counted as non-responders.

Efficacy assessments after the initiation of rescue medication, immunomodulator or violation of protocol-allowed systemic glucocorticoid use will not be included in the analyses. As a result, the subjects will be considered as non-responders in the NRI-MI approach.

- **Mixed-Effect Model Repeat Measurement (MMRM):** MMRM will be the primary approach to the analysis of continuous variables except for glucocorticoid dose. The repeated measures analysis will be conducted using a mixed model including observed measurements at all visits. Subject's observations after intercurrent events will not be used in the MMRM. The mixed model includes the categorical fixed effects of treatment, visit and treatment-by-visit interaction, stratification factors at randomization [Glucocorticoid use at Baseline ( $\geq 10$  mg/day;  $< 10$  mg/day prednisone equivalent); Length of prior glucocorticoid treatment for PMR ( $\leq 1$  year;  $> 1$  year)], and the continuous fixed covariates of baseline measurement. An unstructured variance-covariance matrix (UN) will be used. If the model does not converge, an alternative variance-covariance structure matrix (e.g., autoregressive (1) or compound symmetry) will be used. Parameter estimation is based on the assumption of data being missing at random and the method of restricted maximum likelihood (REML) will be used.
- **Analysis of covariance (ANCOVA):** ANCOVA will be the primary approach for the analysis of glucocorticoid dose. No intercurrent event will be considered in the analysis of glucocorticoid dose. The ANCOVA model includes the categorical fixed effects of treatment and stratification factors at randomization [Glucocorticoid use at Baseline ( $\geq 10$  mg/day;  $< 10$  mg/day prednisone equivalent); Length of prior glucocorticoid treatment for PMR ( $\leq 1$  year;  $> 1$  year)], and baseline glucocorticoid dose as a covariate.
- **As Observed (AO):** The AO analysis will not impute values for missing evaluations, and thus a subject who does not have an evaluation on a scheduled

visit will be excluded from the AO analysis for that visit. AO will include all values collected in the study.

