**9.4 Secondary Efficacy Endpoints and Analyses**

**9.4.1 Secondary Efficacy Endpoints**

The categorical secondary endpoint is

- Achievement of flare-free state up to Week 24

The continuous secondary endpoints are

- Cumulative glucocorticoid dose by 24 weeks

- Change from Baseline in glucocorticoid dose at Week 24

For the analysis of glucocorticoid dose, all systemic glucocorticoid use will be included regardless of the indication.

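### SAP 9.7 compares arms on Week 24 glucocorticoid dose change within groups defined by Week 24 glucocorticoid status; if 'free' means 0 mg, the difference in the free group is 0 with zero standard error whatever the drug does

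*SAP*

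**What the plan says.** SAP 9.7 lists baseline subgroups for the primary endpoint. It then adds that "change from Baseline in glucocorticoid dose at Week 24 will be analyzed by the following subgroup", namely "Glucocorticoid status at Week 24 (glucocorticoid free; not glucocorticoid free". The method is ANCOVA within each subgroup, and "Treatment difference and corresponding confidence interval will be used to summarize the result". Protocol 7.4 names the same endpoint and subgroup, without the request for a difference and interval. Neither document defines glucocorticoid free.

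The only ANCOVA specified for glucocorticoid dose is in SAP 9.2.2, and Protocol 7.4 agrees with it. It contains treatment, the two stratification factors, and "baseline glucocorticoid dose as a covariate". For these endpoints "all systemic glucocorticoid use will be included regardless of the indication" (SAP 9.4.1), and "No intercurrent event will be considered in the analysis of glucocorticoid dose" (SAP 8.0). Protocol 5.8 has the taper reach 0 mg by Week 24 in every subject.

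The one safeguard in SAP 9.7 is a size rule: a subgroup holding less than 10% of subjects is not analysed.

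**The concern.** The other SAP 9.7 subgroups are fixed before treatment starts. This one is read off the outcome being analysed, at the same visit. Two things follow.

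- In the free group, if free means 0 mg, the outcome is an exact function of the covariate and no variation is left for treatment to explain. The planned row would show 0 (0, 0) for every dose. A reader could take that as no benefit among subjects who came off glucocorticoids, when it carries no information about the drug.
- In the not-free group the estimate exists, but the drug may change who is in the group. Placebo subjects still on glucocorticoid and 340 mg subjects still on glucocorticoid are not comparable by randomisation.

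The useful quantity, how many subjects on each dose are at 0 mg at Week 24, is in neither endpoint list (SAP 3.2 and 3.3). The flare-free endpoint does not supply it. After a flare, "glucocorticoid rescue should be administered with the dose and subsequent tapering at the discretion of the investigator" (Protocol 5.8), so a subject who flared may be back at 0 mg. After study drug is stopped, "Prednisone/prednisolone may then be prescribed by the investigator" (Protocol 5.5), so a subject may be on glucocorticoid without a flare.

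**Working it through.** The plan gives no figure to reproduce here.

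**Inputs.** Baseline dose B of 5 to 15 mg/day (Protocol 5.1, criterion 23); 160 subjects in 4 arms; the ANCOVA of SAP 9.2.2.

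**Free group, 0 mg reading.** Let D be the Week 24 dose and Y = D - B.

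1. D = 0 for everyone in the group, so Y = -B.
2. The model is Y = a + t1·(40 mg) + t2·(150 mg) + t3·(340 mg) + s1·(dose stratum) + s2·(duration stratum) + b·B + error, with 7 parameters.
3. Setting b = -1 and all else to 0 gives a residual sum of squares (RSS) of 0. This is the least-squares solution, and the only one if all arms are present and B varies within strata.
4. Residual variance = 0/(n - 7) = 0, so each treatment difference is 0, its standard error is 0, and the interval is (0, 0).

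The size rule does not prevent this: 10% of 160 is 16 subjects, about 4 per arm, leaving 16 - 7 = 9 residual degrees of freedom.

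Numerical check by ordinary least squares:

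| Free subjects | RSS | Slope on B |
|---|---|---|
| 16 | 7e-29 | -1 |
| 75 | 3e-27 | -1 |
| 110 | 2e-26 | -1 |

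Across 500 further simulated trials the largest treatment coefficient was 1.4e-14 and the largest standard error 7.3e-15, which is rounding error. Dropping the covariate does not rescue the analysis. In one simulated trial with 83 free subjects, 340 mg versus placebo was then -0.42 (SE 0.63), which reflects only baseline-dose imbalance among those who happened to be free.

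**Free group, other readings.** The exact zero goes away, but the selection does not.

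- Free of PMR glucocorticoid only, assuming 2%, 5% or 10% of 100 free subjects take 5 mg/day for another reason: mean standard error for 340 mg versus placebo 0.19, 0.31 and 0.44 mg/day.
- Free allowing 0 to 2 mg (illustrative): 0.16 (SE 0.17) in one simulated trial.

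**Not-free group.** Every input here is assumed. Subjects have a latent severity z (standard normal). The most severe 50% on placebo and 25% on drug are not free. Their dose is 6 + k·z, less delta on drug, plus noise with SD 1.5, limited to 1 to 15 mg/day. The mean of z is 0.798 above the median and 1.271 above the 75th percentile. Ignoring the limits:

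- not-free difference = k × (1.271 - 0.798) - delta
- ITT difference = 0.25 × (6 + 1.271k - delta) - 0.50 × (6 + 0.798k)

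For k = 2 and delta = 0 these give +0.95 and -1.66. Simulation with the limits applied (400,000 per arm):

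| k | delta | ITT difference (mg/day) | Not-free difference (mg/day) |
|---|---|---|---|
| 0 | 0 | -1.50 | 0.01 |
| 2 | 0 | -1.65 | +0.95 |
| 2 | 2 | -2.16 | -1.05 |
| 0 | 2 | -1.99 | -1.98 |

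With not-free shares of 60% and 20% the last column ran from -1.99 to +1.51; with 50% and 35%, from -2.00 to +0.52. The subgroup figure can be nil, reversed or close to the ITT figure, depending on quantities the trial does not observe.

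**The case against.** **The weight is small.** This is one subgroup display of one secondary endpoint in a Phase 2 trial without overall Type I error control, and no decision rule uses it. A row of 0 (0, 0) or a software warning largely exposes itself. This stands, and it limits the severity. It does not make the planned analysis meaningful, and the not-free row would not expose itself.

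**The exact zero depends on an undefined term.** It does. A low-dose threshold or a PMR-only definition would remove it. Against that, the taper ends at 0 mg by Week 24, the endpoint counts all systemic use, and Protocol 5.4 allows short-term systemic use for non-PMR reasons only after Week 24. Protocol 6.2 leaves some room through glucocorticoid for adrenal insufficiency. Selection on a post-randomisation outcome remains under every definition.

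**The not-free simulations rest on invented inputs.** They do. They show only that the direction cannot be known in advance, and no bias estimate is claimed.

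**The remedy goes beyond the defect.** Removing the treatment difference is enough to cure the error; the responder table is an addition. It is recommended because it answers the question the subgroup seems meant to address. Counting a missing dose as not free does depart from the SAP's default of multiple imputation for COVID-19 missingness. The departure is small: it is ordinary non-responder imputation, and SAP Appendix C gives no imputation seeds for a dose-based endpoint.

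**Conclusion.** The concern holds. With free meaning 0 mg on the endpoint's own basis, and with the only dose ANCOVA the documents specify, the treatment difference in the free group is 0 with interval (0, 0) by algebra. This needs no assumption about effect, sample size or distribution. In the not-free group the arm comparison is not protected by randomisation, and the direction of the distortion is not established. The number of subjects in each group cannot be read from the flare-free assumptions and is not estimated here. The flaw is confined to this subgroup analysis, so it should be corrected but does not threaten the trial's main conclusions.

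**What to change.** 1. Remove from SAP 9.7 the ANCOVA treatment difference and interval by Week 24 glucocorticoid status.
2. Report instead, in all ITT subjects, the proportion with a Week 24 dose of 0 mg by arm, each dose against placebo, using the stratified CMH test of SAP 9.4.2.
3. Define 0 mg from the recorded dose of all systemic glucocorticoid, under the treatment-policy approach already set for dose (SAP 8.0 and Table 2). Do not set subjects to non-responder after rescue. Count a missing Week 24 dose as not free, and say that this replaces the multiple-imputation default for this table.
4. Show Week 24 dose by arm among subjects with a recorded dose above 0 descriptively only, with the number missing and no treatment difference or interval.
5. Align Protocol 7.4 at its next amendment, and note the difference in the SAP until then.

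The cost is SAP wording and one table from dose data already collected. The protocol line needs IEC/IRB approval (Protocol 8.1), so it is best carried with other changes.
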